- Has restless leg syndrome (based on the *Duke Structured Interview for Sleep Disorders* (DSISD); Edinger, Wyatt, & Olsen, 2009), and that sleep disorder is the primary cause of their sleep complaint (participants with restless legs syndrome who also have insomnia disorder can be included in the study);
- Has an organic cause of sleep disruption that cannot be addressed by cognitive-behavioral changes (e.g., hyperthyroidism), as determined by the DSISD;
- Has excessive daytime sleepiness, defined as a score >15 on the Epworth Sleepiness Scale (ESS) or as determined by the DSISD;
- Does not complete sleep diary assessments within 6 hours of rising on at least 5 of the 7 days of the initial assessment period; or
- Cancels or no-shows for two or more Time 1 assessment appointments

- Has uncontrolled hypertension (screening office BP > 160/100 mm Hg)

Participants who cannot complete study procedures may be withdrawn by the PIs. If any participant is excluded due to uncontrolled hypertension seeks treatment and their blood pressure becomes adequately controlled {e.g., with a stable antihypertensive medication regimen}, they will become eligible to participate if their clinic/office blood pressure is lower than 160/100 mm Hg and they have been stable on their antihypertensive medication(s) for one month.

Because the physiological changes of pregnancy may impact study outcome, we will exclude women who self-report pregnancy. Urine samples will be assayed by a trained staff member using a Quidel QuickVue pregnancy test. These pregnancy tests will be completed for women of childbearing potential. We have developed a short interview for female participants; this interview will help us determine which female participants must have a urine pregnancy test, and when the test should be done. Female participants of childbearing potential who are not pregnant must agree to use appropriate contraception during the course of the study, and to notify study staff if they become pregnant during the study.

Dropout rates across psychological and pharmacologic studies in our clinic that involved 3 to 15 visits have ranged from 0 to 20%. Participants who drop out will receive partial reimbursement for the time they donate. Eligible participants will be randomized to either CBT-I, or CCC+ in a 2:1 ratio. Randomization will be stratified by gender and smoking. Participants will be paid \$1060 for their complete participation.

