
C.5.4. Measurement of Other Potential Covariates. Menopausal status will be documented by self-reported menstrual bleeding, using the criteria described by Tom and colleagues (2010). Status categories are postmenopausal (natural or surgical), perimenopausal, and premenopausal. Menopausal status and lifetime alcohol use disorder (as well as current alcohol consumption measured as drinks per week) will be considered as potential covariates in analytic models. Pain will be measured with the 3-item PEG, a reliable and valid brief version of the Brief Pain Inventory (Krebs et al., 2009). For descriptive and analytic purposes, each patient's medications will be recorded and classified as: anticholinergic; alpha-adrenergic blockade; beta-blockade and other anti-hypertensive medications (diuretics, ACE inhibitors, and calcium channel blockers); specific serotonin re-uptake inhibitor (SSRI);

heterocyclic antidepressant; lithium; MAOI anti-depressant; other antidepressant; neuroleptic; or sedative-hypnotic. This classification system is based on our previous work involving the input and consensus of our team physicians ([name] et al., 2000).

C.6. Measures of Cardiovascular Disease Risk

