The study is designed as a two-arm trial to examine the effects of CBT-I on objective sleep parameters and CVD risk biomarkers. Statistical analyses will be performed using SAS, version 9.4 (SAS Institute, Cary, NC) and Mplus, version 7 (Muthén & Muthén, 2012). The first step in the analysis will be to calculate descriptive statistics, including graphical displays, to summarize all study variables. We will construct individual and mean trajectory plots of the longitudinal outcome variables to understand their general trends from baseline to post-intervention and 6-month follow-up. In addition, we will explore the variability and correlation structure of the longitudinal outcome variables. We will stratify by trauma exposure (combat or non-combat) and objectively measured sleep duration (<6 hours or \geq 6 hours).

Each of the study hypotheses will be examined using data collected at baseline, immediately following the 8-week intervention phase (i.e., post-intervention), and again at 6-month follow-up. Given nesting of these multiple observations within each participant, multilevel modeling (MLM) will be used to examine each set of hypotheses. MLM is a technique for analyzing repeated observations of data across multiple individuals (Searle, Casella, & McCulloch, 1992). Unlike repeated-measures ANOVA,

MLM uses all available data and can handle data missing at random. MLM can also accommodate imbalanced data and unequal variances.

To manage the problem of random positive findings when making multiple comparisons within each hypothesis (i.e., random significant findings occurring due to multiple proposed analyses), we will correct alpha using the “false discovery rate approach” described by Glickman (Glickman, Rao, & Schultz, 2014). This methodology differentiates random findings from hypothesis-driven outcomes and is more powerful than Bonferroni-type alpha adjustments that control the false-positive rate (Benjamini, 2010; Glickman, Rao, & Schultz, 2014; Schafer & Olsen, 1988; Searle, Casella, & McCulloch, 1992; Simes, 1986). Specifically, alpha correction will be applied to Aims 1 and 2 but not to the Supplemental Aim, given that any exploratory hypothesis that is supported would require validation with further research.

D.2. Missing Data Considerations

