MLM can accommodate data missing at random, using maximum likelihood-derived estimates based on all available data. That said, data may be missing not at random (MNAR). That is, the outcome data may be systematically missing, for instance, from participants who experience no benefit from CBT-I. Nevertheless, even in the case of MNAR data, estimates derived from analyses examining Hypothesis 2 (addressing the within-person associations of change in insomnia with change in CVD risk) and the Supplemental Aim are unlikely to be affected by data missingness. After all, even if participants who benefit the least from CBT-I drop out of the study, we still anticipate observing the same magnitude of association between improved sleep and changes in cardiovascular biomarkers and QoL. By contrast, Hypothesis 1, which examines clinical response to CBT-I, would be affected by MNAR data. As such, we will conduct sensitivity analysis on three missing data approaches for Aim 1. First, we will conduct a completer analysis, analyzing only data from participants who complete each of the three assessments. Second, we will allow the maximum-likelihood estimation to generate estimates for all available data. In a third approach, we will use an intent-to-treat approach, assuming that missing post-intervention and/or 6-month follow-up data are evidence of stagnation. Specifically, we will use last observation carried forward in the cases of missing data.

D.3. Primary and Secondary Analyses

To examine the degree to which CBT-I is associated with improved sleep efficiency and insomnia severity index score (manipulation check), linear MLM will be used to model sleep outcomes as a function of treatment (CBT-I, control), time (baseline, post-intervention, 6-month follow-up), and the interaction between treatment and time. Planned treatment contrasts in change from baseline to post-intervention and 6-month follow-up will be examined within the context of the model. To determine the degree to which CBT-I is associated with improved CVD risk biomarkers (Hypotheses 1a), each of the 6 CVD risk variables (24-hr SBP, nighttime SBP dipping, FMD, 24-hr epinephrine, and norepinephrine) will also be modeled as a function of treatment, time, and their interaction, with planned treatment contrasts in change from baseline at post-intervention and 6-month follow-up. Dichotomized 10-year ASCVD risk scores (Hypothesis 1b) and QoL scores (Hypothesis 1c) will similarly be modeled via logistic MLM.

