To examine whether increased sleep efficiency is associated with decreased CVD risk (Hypothesis 2), lagged values will be used to create changes scores, defined by subtracting values for sleep efficiency and each of the CVD risk parameters measured at time $t-1$ from those measured at time t . Thus, decreases will be reflected by negative change scores and increases by positive change scores. Linear MLM will then be used to model each of the change scores corresponding to the 6 aforementioned CVD risk variables using the general equation below:

$$\text{CVD risk}_{\Delta t} = B0 + B1 * \text{Sleep efficiency}_{\Delta t} + B2 * \text{CVD risk}_{t-1} + B3 * \text{Sleep efficiency}_{t-1}$$

where change in the CVD risk outcome from $t-1$ to t will be modeled as a function of corresponding change in sleep efficiency, covarying for sleep efficiency measured at $t-1$ and the outcome in question measured at $t-1$. To explore the heterogeneity of CBT-I treatment response on sleep (Supplemental Aim), potential moderators (trauma type, insomnia phenotype, medication use, biological sex, and minority status) of the effect of CBT-I treatment on sleep outcomes will be examined via interaction effects. Specifically, sleep efficiency and sleep quality measured at baseline, post-intervention, and 6-month follow-up will be modeled in separate analyses as a function of treatment, time, a given moderator, and their second- and third-order interactions. To avoid the effects of multicollinearity, each moderator will be tested in a separate analysis. To determine whether the effect of changes in sleep efficiency on changes in CVD risk parameters vary by each of the aforementioned moderators, the analyses specified above for Hypothesis 2 will be modified to examine the main effect of a given moderator as well as the interaction effect of the moderator and sleep efficiency on each of the CVD risk variables.

D.4. Sample Size and Power Considerations

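### Randomisation is stratified by gender and smoking, but the Aim 1 models omit both factors; precision is lost only to the extent that these factors predict change from baseline.

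*Combined protocol and SAP*

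**What the plan says.** On allocation, C.3 (Patient Eligibility and Randomization) is explicit: "Randomization will be stratified by gender and smoking", with a 2:1 ratio.

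On analysis, D.3 (Primary and Secondary Analyses) states that the cardiovascular biomarkers "will also be modeled as a function of treatment, time, and their interaction, with planned treatment contrasts in change from baseline" at the two later visits. The sleep outcomes have the same three terms, and "Planned treatment contrasts in change from baseline to post-intervention and 6-month follow-up will be examined within the context of the model". Dichotomised ASCVD risk and the quality-of-life scores "will similarly be modeled via logistic MLM". Neither gender nor smoking is a term in any of these models.

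No other section fills the gap. C.5.4 says that menopausal status and alcohol measures "will be considered as potential covariates in analytic models", without naming gender or smoking. Biological sex enters a model only as an exploratory moderator under the Supplemental Aim. Smoking enters no model, although C.6.4 lists current smoking as an input to the ASCVD score.

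A second use of the word stratify appears in D.1 (General Considerations and Descriptive Analyses): "We will stratify by trauma exposure (combat or non-combat) and objectively measured sleep duration", with a cut at 6 hours. The sentence does not say whether it refers to description, subgroup analysis or allocation.

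**The concern.** Balancing allocation within strata removes between-stratum variation from the true sampling error of the arm difference. A model without the strata leaves that variation in its estimated standard error. Where the strata are prognostic for the quantity tested, the intervals are then too wide, the true type I error is below nominal, and some of the precision that stratification could give is not recovered. The plan is also silent on whether the allocation factors belong in the analysis, which leaves room to choose between adjusted and unadjusted results after the data are seen.

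**Working it through.** **1. The plan's own figures (D.4).** Inputs: 150 participants, 3 visits, ICC 0.50, 10% attrition at each later visit, 2:1 allocation, two-sided alpha .05, 80% power.
- Effective sample size without attrition: 150 × 3 / (1 + 2 × 0.50) = 225, as stated.
- With attrition, 121.5 participants have three visits, 13.5 have two and 15 have one: 121.5 × 3/2 + 13.5 × 2/1.5 + 15 = 182.25 + 18 + 15 = 215.25 (stated 215).
- Detectable d with 215/3 = 71.7 control and 143.3 CBT-I units: (1.960 + 0.842) × √(1/71.7 + 1/143.3) = 2.802 × 0.1447 = 0.405 (stated 0.41).

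The figures reproduce. No covariate enters them.

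**2. Factors that shift only the level.** In the linear model, a constant gender or smoking difference is the same at every visit and drops out of a contrast in change. This was checked by simulating a three-visit random-intercept model: N = 150, ICC 0.50, 10% attrition per visit, no treatment effect, 1,500 trials per setting. Two assumptions are not in the documents: permuted blocks of six within four strata, and factor prevalences of 60% and 25%. The entries are type I error for the post-intervention / 6-month contrasts.

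| Share of level variance explained | Factors omitted | Factors as main effects |
|---|---|---|
| 0 | 0.055 / 0.051 | 0.055 / 0.049 |
| 0.2 | 0.048 / 0.049 | 0.049 / 0.047 |
| 0.4 | 0.051 / 0.051 | 0.051 / 0.055 |

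The simulation standard error is √(0.05 × 0.95 / 1,500) = 0.006. All entries agree with 0.05, so there is no conservatism, and main effects alone change nothing.

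**3. Factors that predict change.** Let R² be the share of variance in change that the two factors explain. With close balance within strata, true SE = √(1 − R²) × unadjusted SE. Then:
- True size = 2[1 − Φ(1.960/√(1 − R²))].
- If an effect has 80% nominal power without adjustment, power is Φ(0.842/√(1 − R²)) unadjusted and Φ(2.802/√(1 − R²) − 1.960) adjusted.
- If instead 80% is set for the adjusted test, unadjusted power is Φ(2.802 − 1.960/√(1 − R²)).

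| R² (assumed) | 1.960/√(1 − R²) | True size | Power, unadjusted v adjusted | Unadjusted power when adjusted = 80% |
|---|---|---|---|---|
| 0 | 1.960 | 5.0% | 80.0 v 80.0% | 80.0% |
| 0.02 | 1.980 | 4.8% | 80.2 v 80.8% | 79.4% |
| 0.05 | 2.011 | 4.4% | 80.6 v 82.0% | 78.5% |
| 0.10 | 2.066 | 3.9% | 81.3 v 84.0% | 76.9% |

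On either anchor the gain from adjustment is about 0.6, 1.4 to 1.5, and 2.7 to 3.1 points. A two-visit change-score simulation agrees on size: 0.045 unadjusted and 0.051 adjusted at R² = 0.05, and 0.041 and 0.053 at R² = 0.10.

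**The case against.** The strongest reply is that the omission may cost nothing. Each participant serves as their own baseline in D.3, no document says that gender or smoking predicts change, and any error is towards caution. This stands, and it limits the point to a minor one.

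Four stronger readings are tempting, and the documents support none of them.

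- *The Aim 1 tests are conservative as planned.* That would follow for a single-visit comparison of levels, but D.3 specifies contrasts in change. Under those, size stays near 0.05 however strongly the factors predict level.
- *The trial falls short of its stated 80% power.* D.4 assumes no covariates. Against that calculation the unadjusted test keeps 80.2% to 81.3% for R² of 0.02 to 0.10. Adjustment is a possible gain on the plan, and omitting it leaves no deficit.
- *D.1 contradicts C.3 on the allocation strata.* C.3 names those strata outright. The D.1 sentence follows descriptive plots and correlation structure, does not mention randomisation, and names factors that correspond to two Supplemental Aim moderators, trauma type and insomnia phenotype. It is loosely worded, no more.
- *Smoking feeds the ASCVD score, so the ASCVD test must be distorted.* That shows an effect on level. ASCVD risk is dichotomised and modelled by logistic regression. The linear argument does not carry over to that model, and it was not simulated.

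It may also be said that the title of C.5.4, which speaks of other covariates, implies that the demographic and smoking variables of C.5.3 are covariates too. That is a hint at most and does not prespecify an adjustment.

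**Conclusion.** The omission is real: the factors that define the allocation strata appear in no Aim 1 model. Its cost in the linear models depends entirely on how far gender and smoking predict change. Over an assumed range of 0 to 10% of change variance, true size runs from 5.0% down to 3.9%, and the forgone power from nothing to about 3 points.

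These figures assume close balance within strata, whereas C.3 describes no blocking; looser balance would make the effect smaller. They also refer to a nominal .05 test, whereas D.1 applies a false discovery rate correction to Aims 1 and 2. No size is claimed for the ASCVD and quality-of-life models. The omission does not inflate type I error in the linear tests. Severity is minor, and the change is worth making because it is nearly free and settles the adjustment before the data are seen.

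**What to change.** - **D.3, linear models:** add gender and smoking, coded as for randomisation, each with its interaction with time. The interactions are essential, because main effects alone leave the change contrasts as they are.
- **D.3, logistic models:** include the two factors where cell counts allow, and state the rule in advance. With 50 controls some cells may be sparse.
- **D.1, clarification only:** state that trauma exposure and sleep duration are descriptive or moderator subgroups, and that the allocation strata are those in C.3.

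The cost is a few sentences and a few degrees of freedom: with three visits, one main effect and two time interactions per factor, six parameters in all. No new data are needed, since the demographics form and the nicotine dependence questionnaire are completed at the first screening visit (measures table, C.5).
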